7.3. Early Termination

The ET Visit will be performed for all patients who are prematurely discontinued up to Week 26 from the study; however, patients who decide only to discontinue therapy early will continue to complete trial procedures as per protocol. It is very important to ensure that all procedures, as outlined in the SoA ET visit, are performed in such patients at this visit prior to discontinuing the patient from the trial. Most importantly, a plasma sample for AdV, BKV, CMV, HHV-6, and JCV and a PCMB sample for EBV for PCR testing at the central laboratory should be collected at this visit.

7.4. Lost to Follow up

A participant will be considered lost to follow-up if he or she repeatedly fails to return for scheduled visits and is unable to be contacted by the study site.

The following actions must be taken if a participant fails to return to the clinic for a required study visit:

- The site must attempt to contact the participant and reschedule the missed visit as soon as possible and counsel the participant on the importance of maintaining the assigned visit schedule and ascertain whether or not the participant wishes to and/or should continue in the study.
- Before a participant is deemed lost to follow up, the Investigator or designee must make every effort to regain contact with the participant (where possible, 3 telephone calls and, if necessary, a certified letter to the participant's last known mailing address or local equivalent methods). These contact attempts should be documented in the participant's medical record.
- Should the participant continue to be unreachable, he/she will be considered to have withdrawn from the study.

Discontinuation of specific sites or of the study as a whole are handled as part of Appendix 1 in [Section 10.1.9](#).

8. STUDY ASSESSMENTS AND PROCEDURES

- Study procedures and their timing are summarized in the SoA. Protocol waivers or exemptions are not allowed.
- Immediate safety concerns should be discussed with the Sponsor immediately upon occurrence or awareness to determine if the participant should continue or discontinue study intervention.
- Adherence to the study design requirements, including those specified in the SoA, is essential and required for study conduct.
- All screening evaluations must be completed and reviewed to confirm that potential participants meet all eligibility criteria. The Investigator will maintain a screening log to record details of all participants screened and to confirm eligibility or record reasons for screening failure, as applicable.
- Procedures conducted as part of the participant's routine clinical management (eg, blood count) and obtained before signing of the informed consent form (ICF) may be utilized for screening or baseline purposes provided the procedures met the protocol-specified criteria and were performed within the time frame defined in the SoA.
- Results (eg, Safety/Laboratory/analyte) that could unblind the study will not be reported to investigative sites or other blinded personnel until the study has been unblinded.
- The amount of blood collected from each adult (≥ 18 years) and pediatric patient over the duration of the study are described in the Laboratory Manual. The maximum amount of blood collected, including any extra assessments that may be required, will not exceed 10.5 mL/kg or 550 mL, whichever is smaller, over any eight week period for adult patients.
- For pediatric patients, blood sampling requirements for the study have been minimized by reducing the volume per sample collected (where possible), and by omitting collection at certain timepoints.
- Repeat or unscheduled samples may be taken for safety reasons or for technical issues with the samples.

8.1. Study Periods

8.1.1. Pre-screening visit (optional)

A pre-screening visit will be completed if possible at least 1 week prior to HCT. A separate ICF for pre-screening will be obtained.

8.1.2. Screening period

Screening of potential eligible patients may begin as soon as the day of HCT and within 42 (+7) days after transplantation. Patients will have plasma samples tested for AdV, BKV, CMV, HHV-6, and JCV viremia and PBMCs for EBV viremia using PCR assays weekly during the screening period. Patients should be tested at the first assessment during Screening by the central laboratory for AdV, BKV, CMV, EBV, HHV-6, and JCV viremia using PCR assays for each virus. Patients

will then be tested weekly during Screening until treatment assignment. For initial screening purposes, results of the assay done at a local laboratory will be acceptable; however, a test by the central lab must be done prior to treatment assignment.

8.1.3. Treatment period

The treatment period is 14 weeks. Study therapy (with ALVR105 or placebo) will begin between 15 and 42 (+7) days (inclusive) post-HCT. Study therapy will be given at 2-week intervals through Week 14, and the study evaluation will continue through Week 26 (~6 months). The first 25 to 35 patients (Cohort OL) will be assigned to ALVR105 for 30 days of open-label dosing [REDACTED].

8.1.4. Follow-up period

The follow-up period is for 12 weeks with monthly visits. A telephone follow-up call will occur approximately 12 months (~52 weeks) after Week 26.

8.2. Efficacy Assessments

Planned time points for all efficacy assessments are provided in the SoA (Section 1.3).

8.2.1. Definitions and Determination of Viremia

8.2.2. Viral Load

Samples for viral sequence/genotype will be collected on all patients as indicated in Section 1.3. Viral loads of AdV, BKV, CMV, HHV-6, and JCV in plasma and of EBV in PBMCs will be measured at times specified in Section 1.3. The results of any repeat analyses from screening must be available at the time of treatment assignment, with the exception of patients screened within 7 days of treatment assignment, who would not have more than 1 analysis. [REDACTED]

[REDACTED] Additional post-infusion samples may be collected, as clinically indicated. If patient develops any clinically significant infection of AdV, BKV, CMV, EBV, HHV-6, and JCV at any point during the study periods, infection assessments (Section 8.3) should be followed prior to initiating standard of care therapy.

[REDACTED] Resolution of viral infection will be defined as a return to normal range as defined by the assay used and complete resolution of clinical signs and symptoms as defined in the CAC charter.

Viral load will be quantitated using PCR assays.

8.2.3. Resolution of Viral Infections

In patients who develop viral infections, plasma will be monitored for AdV, BKV, CMV, HHV-6, or JCV viral load and PBMCs will be monitored for EBV. See Section 1.3. Resolution of viral infection is defined in the CAC Charter. Resolution of viral infection will be defined as less than

the lower limit of quantification (LLOQ) and complete resolution of clinical signs and symptoms as determined by the Investigator and the CAC (see Appendix 7, [Section 10.7](#)).

8.2.4. Quality of Life

Quality of life will be measured using the FACT-BMT and the age-appropriate version of the EQ-5D at times indicated in [Section 1.3](#). The FACT-BMT was designed to measure the QoL in patients undergoing bone marrow transplantation. It combines the general Functional Assessment of Cancer Therapy (FACT-G), assessing physical well-being, social/family well-being, emotional well-being and functional well-being, with the Bone Marrow Transplantation Sub-scale (BMTS) to measure BMT-specific concerns ([McQuellon 1997](#)).

The EQ-5D is a group of instruments that was developed to assess patient-reported health-related QoL ([EuroQol Group 1990](#)). The EQ-5D-5L includes the EQ-5D descriptive system and the EQ visual analog scale (EQ VAS). The EQ-5D descriptive system comprises 5 dimensions: mobility, self-care, usual activities, pain/discomfort, and anxiety/depression. In the EQ-5D-5L, each dimension has 5 levels: no problems, slight problems, moderate problems, severe problems, and extreme problems. The patient is asked to indicate his or her health state by checking the box next to the most appropriate statement in each of the 5 dimensions. The versions used in children have 3 responses to each question instead of 5.

In this study, the EQ-5D-5L will be used for individuals ≥ 12 years of age, the EQ-5D-Y for children 8 to 11 years of age, and the EQ-5D-Y Proxy Version 1 for children ≤ 7 years of age. Data for children < 4 years of age will also be collected using the EQ-5D-Y Proxy Version 1, but these results will be analyzed separately from the results for children 4 to 7 years of age.

The EQ-5D-5L, the EQ-5D-Y, and the EQ-5D-Y Proxy Version 1 include the EQ Visual Analog Scale (VAS). The EQ VAS records the patient's self-rated health on a vertical visual analog scale, where the endpoints are labeled "The best health you can imagine" and "The worst health you can imagine."

Quality of life measures should be completed as indicated in the SoA and prior to any study procedures at the visit.

8.2.5. Virus-specific T Cell Assessment

Patient peripheral blood mononuclear cells will be assessed for the presence of each of the viral-specific virus-reactive T cells using enzyme-linked immunospot. See [Section 1.3](#).

8.3. Infection Assessments

Infection assessments will be performed for all patients who, in the opinion of the Investigator, might meet the criteria described in Appendix 8, [Section 10.8](#). It is very important to ensure that all procedures, as outlined in the SoA, are performed for infection assessment immediately prior to the initiation of treatment of viral diseases or initiation of preemptive therapy (ie, on the day anti-viral therapy is initiated).

A symptom checklist should be completed in the infection assessment eCRF.

Patients will continue to be followed in the study and complete all remaining visits through Week 26 as outlined in the SoA.

8.3.1. Confirmatory Plasma Samples for Suspected Infection

Most importantly, a plasma sample for AdV, BKV, CMV, HHV-6, and JCV, and a PBMC sample for EBV for PCR testing at the central laboratory should be collected. Should confirmatory test results from the central laboratory not be available within the timeframe that the Investigator wishes to initiate anti-viral therapy, the Investigator may use a positive local laboratory test result to make the decision. Whenever it is deemed clinically necessary to use a local laboratory, a plasma sample should also be collected and sent to the central laboratory.

8.3.2. Samples When Initiating Anti-viral Therapy

If antiviral therapy is to be initiated, it is mandatory to send a plasma sample for AdV, BKV, CMV, HHV-6, and JCV and a PBMC sample for EBV for DNA PCR testing to the central laboratory immediately prior to (ie, on the day of) initiating treatment for AdV, BKV, CMV, EBV, HHV-6, or JCV disease or preemptive therapy in ALL instances. As clinically indicated, stool, urine, and/or CSF samples should be collected for AdV, BKV, CMV, EBV, HHV-6, and JCV and sent to the central laboratory as feasible (see Appendix 8, [Section 10.8.](#))

When local laboratory test results are used for initiating anti-viral therapy, two plasma (and PBMC for EBV) samples for PCR testing must be sent to the central laboratory. The first sample must be collected immediately prior to (ie, on the day of) initiating anti-viral therapy. The second sample must be collected 48-72 hours after initiating anti-viral therapy. The local laboratory result must also be reported in such instances.

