^g Clinical laboratory assessments collected as part of standard of care may be used to fulfill these requirements. CBC must include differential and LFTs

must include alkaline phosphatase, bilirubin (direct and indirect); GGT, AST, and ALT. Urinalysis must be performed. Laboratory safety evaluations (hematology, chemistry, and urinalysis) specified in [Section 8.4.4](#) will be performed prior to study drug initiation. These samples will be sent to the appropriate central laboratory(ies) following the procedure(s) described in the study manual(s).

^h For female patients, a urine pregnancy test will be performed at the site prior to study therapy initiation. If the urine pregnancy test result is negative, the patient will be eligible for treatment assignment and the remainder of the Day 1 testing/procedures will be performed. If the urine pregnancy result is positive, the patient must not be assigned to treatment and should reflex to a β -HCG blood test before screen failing. A urine pregnancy test will be performed prior to each treatment for female patients who are of childbearing potential.

ⁱ Viral loads of AdV, BKV, CMV, JCV, and HHV-6 in plasma and of EBV in PCMBs will be measured. Additional post-infusion samples may be collected, as clinically indicated. If patient develops any clinically significant infection of AdV, BKV, CMV, EBV, HHV-6, or JCV at any point during the study periods, infection assessments should be followed prior to initiating standard of care therapy (see [Section 8.3](#)).

^j Patients in Cohort OL will be assigned to ALVR105. Patients in Cohorts A and B will be randomized to either ALVR105 or placebo based upon the last viral load assessed and within 7 days of randomization. Treatment assignment will be about 2 to 3 days before Day 1.

^k Patient peripheral blood mononuclear cells will be assessed for the presence of virus-reactive T cells using enzyme-linked immunospot.

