^b Adverse event monitoring should include the collection of all adverse events through follow-up in all patients, including those who have discontinued study treatment but are continuing in the study. Positive pregnancy and partner pregnancy information up to 90 days after last study drug administration will be collected.

^c Viral loads of AdV, BKV, CMV, HHV-6, and JCV in plasma and in PCMBs for EBV will be measured and evaluated at the central lab. Additional post-infusion samples may be collected if clinically indicated. If patient develops any clinically significant infection of AdV, BKV, CMV, EBV, HHV-6, or JCV at any point during the study periods, infection assessments should be completed prior to initiating standard of care therapy (see [Section 8.3](#)).

^d Patient peripheral blood mononuclear cells will be assessed for the presence of virus-reactive T cells using enzyme-linked immunospot.

^e The infection assessment will be performed for all patients who require either treatment for disease or initiation of preemptive therapy during both the primary study period and the follow-up period through Week 26 ([Section 8.3](#)). It is very important to ensure that all procedures, as outlined in the SoA, are performed immediately prior to the initiation of treatment of viral diseases or initiation of preemptive therapy (ie, on the day anti-viral therapy is initiated). Most importantly, a plasma sample for AdV, BKV, CMV, HHV-6, and JCV and a PCMB sample for EBV for PCR testing at the central laboratory should be collected. After developing an infection, such patients will continue to be followed in the study and complete all remaining visits through Week 26.

^f Assessment of quality of life (using FACT-BMT, EQ-5D-5L, EQ-5D-Y, and EQ-5D-Y Proxy Version 1questionnaires, as age-appropriate) should be completed prior to any study procedures at this visit.

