2.2. Background

During the period of immune recovery after allogeneic HCT, viral infections and reactivations, which are normally controlled by T cell immunity, are an important cause of morbidity and mortality. The risk for infection is dictated by a number of factors, including the degree of immunosuppression and the immune status of the donor. Reactivation of latent viruses such as CMV and BKV, or primary infection with a virus such as AdV, has become increasingly prominent. In a study at a large US HCT center, in approximately 90% of allogeneic HCT patients, the suppressed immune system allows viruses that were previously in a latent, quiescent state to reactivate and more than 60% of allogeneic HCT patients experience a reactivation of more than one virus, including BKV, CMV, AdV, EBV and HHV-6 ([Hill 2017](#)). In another recent study of infections following haploidentical allogeneic HCT, Slade, et al documented that 72% of patients

experienced at least one severe viral infection (Slade 2017). Fifteen percent of patients developed CMV infection despite prophylaxis, and 19% developed BK virus-associated –hemorrhagic cystitis. One of 3 children is reported to have an AdV infection within 6 months following allogeneic HCT (Sedláček 2019). Progression to AdV disease is associated with significant morbidity and mortality rates of up to 50% (Zecca 2019). Similarly, Mulanovich and colleagues (2011) reported that, among patients receiving either cord blood or T-cell depleted transplants, viral infections were frequent and the most common cause of death in both groups. Even among T cell-replete transplants using the post-cyclophosphamide protocol, Crocchiolo (2015) reported the incidence of viral infections to be 70%, with CMV and BKV being the most frequent and the most clinically threatening etiologies. The increased risk of mortality in the first 60 days post-transplant was approximately 18 times greater for patients with a CMV viral load ≥ 250 IU/ml (Green 2016).

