10.2. Appendix 2: Clinical Laboratory Tests

- The tests detailed in Table 5: Protocol-Required Safety Laboratory Tests will be performed by the central laboratory.
- Local laboratory results are only required in the event that the central laboratory results are not available in time for either study intervention administration and/or response evaluation. If a local sample is required, it is important that the sample for central analysis is obtained at the same time. Additionally, if the local laboratory results are used to make either a study intervention decision or response evaluation, the results must be recorded.
- Protocol-specific requirements for inclusion or exclusion of participants are detailed in [Section 5](#) of the protocol.
- Additional tests may be performed at any time during the study as determined necessary by the Investigator or required by local regulations.

Table 5: Protocol-Required Safety Laboratory Tests

Clinical Chemistry Panel (Central Laboratory)

Alanine aminotransferase	Albumin
Alkaline phosphatase	Amylase
Aspartate aminotransferase	Bicarbonate
Blood urea nitrogen	Calcium
Chloride	Creatine kinase
Creatinine	Direct bilirubin Gamma-glutamyl transferase
Glucose	Inorganic phosphorus
Lactate dehydrogenase	Lipase
Potassium	Sodium
Total bilirubin	Total protein
Uric acid	

Hematology (Central Laboratory)

Hematocrit	Hemoglobin
Platelets	Red blood cell count
White blood cell count and differential [1]	

1. Manual microscopic review is performed only if white blood cell count and/or differential values are out of reference range.

Viral Load in Blood and Urine (Central Laboratory)

Adenovirus	BK virus
Cytomegalovirus	Epstein-Barr virus
Human herpesvirus 6	JC virus

When viral load determination is performed in the laboratory, residual viral deoxyribonucleic acid (DNA) will be stored for potential viral sequencing and genotyping in the event of recurrent infection.

Viral load determination at screening may be performed at a local or central laboratory for the purpose of determining eligibility/inclusion. If the results from the local laboratory are used for determination of eligibility/inclusion, an additional pre-randomization sample for viruria testing must be collected for assay at the central laboratory. These results do not have to be available at the time of randomization or study treatment infusion. Additional post-infusion samples may be collected, as clinically indicated.

Urinalysis (Local Laboratory)

Bilirubin	Blood

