10.8. Appendix 8: Endpoint Definitions

Infection and disease definitions for AlloVir prevention trial

- The prevention trial has a primary objective of preventing clinically significant CMV, BKV, EBV, AdV, HHV-6, and/or JCV infection and end-organ disease through Week 14 (~100 days) and a secondary objective of preventing clinically significant CMV, BKV, EBV, AdV, HHV-6, and/or JCV infection and end-organ disease through Week 26 (~6 months).
- The definitions below are intended to assist the Endpoint Adjudication Committee with adjudicating cases of infection and disease, but the committee may also use their judgment to adjudicate cases that are not captured by the definitions below (e.g., rare disease manifestations of the viruses).

Manifestation	Definition
HHV-6	
Clinically significant HHV-6 viremia^{1,2}	
 HHV-6 plasma viral load >10,000 copies/mL on one occasion or >1,000 on ≥ 2 occasions separated by at least a week
HHV-6 encephalitis/post-transplant acute limbic encephalitis³	
 Detection of HHV-6 in the CSF coinciding with acute-onset altered mental status (encephalopathy) or short-term memory loss or seizures AND Other likely infectious or non-infectious causes have been excluded AND ciHHV-6 has been excluded 
OR (if lumbar puncture not possible):
 
 Detection of HHV-6 in the plasma >1,000 copies/mL coinciding with acute-onset altered mental status (encephalopathy) or short-term memory loss or seizures AND MRI findings suggestive of HHV-6 encephalitis such as hyperintensities in the limbic system (abnormalities outside the medial temporal lobes are less common) Other likely infectious or non-infectious causes have been excluded AND ciHHV-6 has been excluded
Other	
 Also consider these manifestations as appropriate: delirium/decreased neurocognitive functioning, acute GVHD, bone marrow suppression, elevated LFTs, idiopathic pulmonary syndrome (in setting of HHV-6 detected from BAL fluid)
BK virus	
Clinically significant BK viremia	
 BK virus plasma viral load >100,000 copies/mL or >10,000 copies/mL on ≥ 2 occasions separated by at least a week

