	
OR cytopathic adenoviral effect identified on biopsy
 
OR
 
 • At least 2 suggestive signs or symptoms: diarrhea, abdominal pain, ileus, vomiting, GI hemorrhage AND • AdV isolated from the stool by culture or PCR AND • Other causative agents (e.g., bacterial, viral, amebic) ruled out AND endoscopic evidence of lesions (macroscopic or microscopic) not attributed to GVHD (i.e., biopsy-proven)
Adenovirus pancreatitis⁶	
 • Consistent clinical and imaging findings such as: 
 ◦ Suggestive signs or symptoms (abdominal pain, GI symptoms) ◦ Amylase or lipase >5xULN ◦ Imaging (eg, CT scan) findings suggesting pancreatitis 
AND
 
 • AdV identified by pancreatic biopsy or ERCP brushings/washings via antigen/IHC or culture OR • AdV detected by plasma PCR AND • Other causes (e.g., gallstones, hypertriglyceridemia, parasites, paramyxovirus, other viruses) ruled out
Adenovirus hemorrhagic cystitis	
 • Clinical signs and symptoms of cystitis, including dysuria, lower abdominal pain, and/or other bladder-associated pain or spasms AND 
 • Grade ≥ 2 hematuria (per Bedi scale) AND • AdV viruria of $>5 \log_{10}$ copies/mL AND • No other cause for the HC is apparent
Adenovirus nephritis	
 • At least one of the following: 
 ◦ Suggestive signs or symptoms (impaired renal function, proteinuria, microscopic hematuria, hypertension, dysuria) ◦ Enlarged kidney on imaging ◦ Renal/bladder obstruction AND • AdV identified via renal biopsy via antigen/IHC or culture OR • AdV detected by urine PCR +/- plasma PCR and other causes (e.g., BK virus, JC virus, bacterial and drug-induced) ruled out
Adenovirus encephalitis/myelitis⁶	
 • At least one of the following signs/symptoms of encephalitis: 
 ◦ Abnormal CSF ◦ Focal CNS deficit ◦ Cognitive impairment ◦ Visual symptoms ◦ Seizure ◦ Evidence of compatible lesions by CT scan or MRI

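### The BKV and AdV hemorrhagic cystitis definitions require a urine viral load that no visit schedule or named infection-assessment sample collects, so ascertainment depends on discretionary sampling

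*Protocol*

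**What the plan says.** Protocol Appendix 8 (Section 10.8) builds hemorrhagic cystitis from four elements, all required: bladder symptoms, hematuria of at least Grade 2 on the Bedi scale, viruria above 5 log10 copies/mL, and no other apparent cause. The BKV and AdV entries have the same structure; the third element of the latter begins "AdV viruria of". Appendix 8 defines no other BKV end-organ disease.

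The viral load samples are described elsewhere. For the treatment period the schedule footnotes say "Viral loads of AdV, BKV, CMV, JCV, and HHV-6 in plasma and of EBV in PCMBs will be measured"; for follow-up they say "Viral loads of AdV, BKV, CMV, HHV-6, and JCV in plasma and in PCMBs for EBV will be measured and evaluated". Section 8.3.1, on suspected infection, says "Most importantly, a plasma sample for AdV, BKV, CMV, HHV-6, and JCV, and a PBMC sample for EBV" should go to the central laboratory. Section 8.3.2 makes the same two specimens mandatory when an antiviral is started and adds "As clinically indicated, stool, urine, and/or CSF samples should be collected", to be sent to the central laboratory as feasible.

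Table 5 in Appendix 2, titled as protocol-required safety tests, has a panel headed "Viral Load in Blood and Urine (Central Laboratory" that covers all six viruses. Section 8.4.4 leaves the timing of Table 5 tests to the laboratory manual and the schedules.

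**The concern.** A required element of a disease definition should have a sample behind it. Here the definition turns on a quantitative urine result, while the text on suspected infection asks for blood. The one request for urine in Section 8.3 is discretionary and is tied to starting an antiviral.

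That trigger fits BKV poorly. Section 2.3.1 counts BKV among the viruses without approved or clearly effective therapy, and Sections 6.8.1 and 6.8.2.1 permit supportive measures such as agents for bleeding, antispasmodics and hydration. A cystitis case managed only in this way has no urine instruction in Section 8.3.

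At stake is whether the cystitis rate reflects the patients or the sites' habits in sending urine. Cystitis contributes to the primary endpoint. It matters more for the Week 14 secondary endpoint restricted to disease, where plasma viremia alone does not count.

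**Working it through.** **1. Is there a urine PCR behind the definition?**

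| Place in the protocol | Specimens for viral PCR | Status of urine |
|---|---|---|
| Tables 1 to 4, viral load rows and footnotes | Plasma; PBMC for EBV | None |
| Section 8.3.1 and the infection-assessment footnotes | Plasma; PBMC for EBV | Not named |
| Section 8.3.2, antiviral started | Plasma and PBMC mandatory | If clinically indicated; to central laboratory as feasible |
| Table 5, viral load panel | Blood and urine, six viruses | Listed, but matched by no schedule row |
| Table 5, note on screening | Pre-randomization viruria sample | Compulsory only if local results were used for eligibility |
| Table 5, same note | Further post-infusion samples | Permitted, not required |
| Table 5, urinalysis | Local urinalysis panel, including blood | No PCR |

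The only compulsory viruria sample precedes treatment and is conditional, so it cannot document disease that arises on study.

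**2. Is there another route to the diagnosis?** Not in the two cystitis entries. Appendix 8 does give alternatives elsewhere: HHV-6 and AdV encephalitis have a route when lumbar puncture is not possible, and AdV hepatitis can rest on plasma PCR or on biopsy.

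**3. Which endpoint is exposed?** A patient with cystitis and no urine result can still be a primary endpoint event through viremia. For BKV this needs plasma above 100,000 copies/mL, or above 10,000 on at least two occasions a week or more apart. For AdV it needs a single value above 10,000, or two consecutive and rising values above 1,000. Neither route serves the disease-only endpoint.

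**4. How large could the loss be?** There is no planned figure to reproduce: the visible text of Section 9.2 gives no rate or power. The only rate is in Section 2.2, where in a cited haploidentical series "19% developed BK virus-associated" hemorrhagic cystitis; no numerator or denominator is given. As illustration, let

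- p = 0.19 (that series);
- s = share of cases with a quantitative urine result (assumed);
- N = 25, 30 or 35. The open-label (OL) cohort of 25 to 35 is the only visible cohort size and is used here only for scale.

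Expected cases are N × p: 25 × 0.19 = 4.75; 30 × 0.19 = 5.70; 35 × 0.19 = 6.65. The rate meeting the written definition is p × s, and the cases lost are N × p × (1 − s).

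| s | Rate meeting definition | Points lost | Cases lost, N = 25 / 30 / 35 |
|---|---|---|---|
| 0.90 | 17.1% | 1.9 | 0.5 / 0.6 / 0.7 |
| 0.75 | 14.25% | 4.75 | 1.2 / 1.4 / 1.7 |
| 0.50 | 9.5% | 9.5 | 2.4 / 2.9 / 3.3 |

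For the primary endpoint, let v be the share of unsampled cases that also meet the BK viremia criterion. The loss is p × (1 − s) × (1 − v). With s = 0.75 and v = 0.5 (both assumed) it is 0.19 × 0.25 × 0.5 = 2.4 points, against 4.75 for the disease-only endpoint. The documents give neither s nor v.

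**The case against.** **The definitions are guidance.** Appendix 8 says they help the committee, and that "the committee may also use their judgment to adjudicate cases that are not captured by the definitions below". A reader might infer that an unsampled case cannot be scored at all; this clause rules out so absolute a reading. It is only a partial answer, though. Its example is rare manifestations, whereas cystitis is a defined disease, and judgment cannot supply a missing viral load.

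**Urine would often be sent anyway.** Symptomatic cystitis with hematuria is a natural clinical indication. The list in Section 8.3.1 is not worded as exhaustive. The definitions name no laboratory, so a local quantitative result could serve. The laboratory manual and the committee's charter are not available and may schedule urine. All this may make the loss small, but nothing in the protocol secures the result.

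**A missing sample is not stated to be a non-event.** A reader might infer that it is scored as no disease. No section says so. SAP Section 3.1.5 presents data as observed without imputation, and the committee's handling of an incomplete element is not visible.

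**The OL cohort works differently.** A reader might infer that the OL results are understated by this route. SAP Section 1 says the investigators determined those events. SAP Section 3.4.1 defines an event without a viruria threshold, and the SAP has no disease-only endpoint. Protocol Section 8.3 does point investigators to Appendix 8 when deciding whom to assess, but the threshold is not shown to bind in this cohort.

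**The 19% is not the trial's rate.** It is a background figure for BKV in haploidentical transplants. It says nothing about AdV, is not a design assumption, and does not cover the other high-risk donor groups. This objection stands in full.

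**Conclusion.** The gap is real. Followed as written, the protocol can leave uncollected a required element of the only BKV end-organ disease it defines, and of AdV cystitis. Table 5 and the schedules also disagree on whether urine viral load is a required test. A case without a quantitative urine result cannot meet the written definition unless the committee uses its judgment, and a case managed without antivirals is the most exposed.

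The consequence is ascertainment that depends on discretionary sampling, mainly for the protocol's Week 14 disease endpoint. The size is unknown. The 1.9 to 9.5 points rest on three assumptions: that 19% applies, that 10% to 50% of cases lack a result, and that the definition is applied literally. They show scale and are not an estimate for this trial. The documents do not support treating 19% as an expected event rate or concluding that the OL results are biased. This is a worthwhile, inexpensive correction rather than a threat to the primary analysis.

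**What to change.** - In Sections 8.3 and 8.3.1, require a urine sample for quantitative BKV and AdV PCR at every infection assessment with cystitis symptoms or visible hematuria, whether or not an antiviral is started.
- Reconcile Table 5 with the schedule tables, for example with a footnote to the infection-assessment row, so that both say when urine viral load is required.
- Report the number of cases that satisfy the other cystitis elements but have viruria not assessed. This needs the Bedi grade on record; Section 8.3 already has a symptom checklist, whose fields should be checked for it.

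The sampling change serves patients still to be enrolled, in Cohorts A and B. OL follow-up is done, so only the not-assessed count can be added there, as far as the collected data allow.

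The cost is one non-invasive urine tube per suspected episode, sent to a central laboratory to which Table 5 already assigns the test, plus a few lines of protocol text and one line in a table.
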